**Data analysis**

SPSS will be used for statistical analysis. All outcome measures will be analyzed using one-way ANOVA.

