**DATE: - 04/07/2022**

## **Introduction and Background**

Frozen shoulder is characterized by painful limitation of active and passive range of motion (ROM) of the shoulder. People describe pain, which can be severe, an inability to sleep on the affected side, loss of shoulder function in activities of daily living and limited movements that can lead to chronic stiffness.

Physiotherapy is one of the main treatments which aims to reduce pain, and regain mobility, muscle strength and optimal daily function. There is global loss of both passive and active ROM of the glenohumeral joint, with external rotation usually being the most restricted physiologic movement. Although frozen shoulder is frequently described as a self-limiting condition with gradual spontaneous recovery, the condition typically has mean duration of 30 months.

Individuals with primary frozen shoulder are commonly between 40 and 65 years old, and the incidence appears 4 times higher in females than males. The condition generally presents unilaterally with the non-dominant shoulder more commonly affected.

Frozen shoulder is “a condition difficult to define, difficult to treat, and difficult to explain from the point of view of pathology(Codman 1935) . The term adhesive capsulitis was introduced by Nevaiser to describe the inflamed and fibrotic condition of the capsule sticking to the humerus. But this term does not appear to appropriately describe the condition and arguably term should be abandoned as explained by Lundberg (1979).

The etiological explanation of frozen shoulder was directed toward two theories, contraction of the capsule and adhesions of the capsule which were running parallel. Some histological findings show that there is contraction of the capsule. In 1969, Lundberg came with the term frozen shoulder syndrome. In 2014, Jeremy Lewis came out with the term frozen shoulder contraction syndrome. It is likely that limitations in range of motion and the pain associated with frozen shoulder are not only related to capsular and ligamentous tightness, but also fascial restrictions, muscular tightness, and trigger points within the muscles. Physical therapists can address impairments and limitations associated each of these contributors to the pathology of frozen shoulder with a variety of treatment methods.

A meta-analysis suggested that glucocorticoid injections combined with exercise and manual therapy may provide improvement in range of motion .

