## **Objective**

The objective of this study is to compare the effect of heavy slow resistance exercises with conventional physical therapy alone for the management of frozen shoulder using double-blind randomized controlled trial design.

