## **Sample size**

Shoulder external rotation range of motion is considered as the primary outcome measure for the proposed study. A study by Celik (2010) [24] was used to inform the sample size calculation, where the shoulder external rotation was measured at baseline and at 12-week post intervention for the glenohumeral range of motion exercise group. Using the means and standard deviations of 22 (12.5) degrees and 33 (14.9) degrees for external rotation range of motion changes resulted in an effect size of -0.799. With a two tailed hypothesis, the minimum required sample size is 30 patients per group at ( $\alpha$ ) 0.05 and a power (1-  $\beta$ ) of 85%. 35 participants per group will be recruited to account for attrition.

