## **Randomization/Blinding**

Participants will be randomly assigned following simple envelope randomization procedures to one of the two treatment groups. Patients will be blinded from the treatment group, and the examinations will be performed by a blinded examiner.

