## **Intervention**

Both groups will receive conventional therapy sessions which include active ROM exercise, strengthening and stretching exercises, end-range mobilization and hot packs (if indicated). Exercises will be given within the pain threshold limit twice a week for 12 weeks. In addition, the experimental group will receive heavy slow resistance exercise program using a theratube. The exact management approach will be standardized between the two groups in terms of intensity and frequency and the experimental group will only receive additional heavy slow resistance exercise.

Subjects will be assessed at baseline and at 3, 6, and 12 months. Shoulder external rotation and abduction ROM will be measured and compared within and between groups and will be analyzed using a One-way ANOVA.

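### One-way ANOVA is fixed for every outcome: it is the wrong test for change within a group over four visits, and between groups it is valid but ignores the baseline

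*Protocol*

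**What the plan says.** The Data analysis section names one method for everything: "All outcome measures will be analyzed using one-way ANOVA". The Intervention section sets the visit schedule, "Subjects will be assessed at baseline and at 3, 6, and 12 months", and says that external rotation and abduction "will be measured and compared within and between groups and will be analyzed using a One-way ANOVA". Patients are randomized "to one of the two treatment groups".

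The Objective is a between-group question: "to compare the effect of heavy slow resistance exercises with conventional physical therapy alone for the management of frozen shoulder".

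The Sample size section relies on a published study in which "the shoulder external rotation was measured at baseline and at 12-week post intervention", and describes its two means and SDs as being "for external rotation range of motion changes resulted in an effect size of -0.799". The word for change appears there, but neither analysis statement mentions a change score. Nowhere does the protocol name a patient effect, a repeated-measures term, a baseline covariate or a primary visit.

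**The concern.** Two different comparisons are given the same test.

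- **Within a group.** The four visits come from the same patients. One-way ANOVA assumes independent observations, so stable differences between patients stay in the error term. With positive correlation between visits the p-values are too large, and real change over time can be missed.
- **Between groups.** At a single visit, one-way ANOVA with two groups is the two-sample t-test. Randomization makes it valid. The cost is precision: a baseline measurement that every patient provides is left out of the comparison, in a trial of only 70.

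The protocol does not say that visits will be pooled as separate rows in the between-group test, so no inflation of false positives is claimed.

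**Working it through.** **Inputs.** From the Sample size section: means 22 and 33 degrees, SDs 12.5 and 14.9, two-sided alpha 0.05, power 85%, 30 per group (35 recruited). From the Intervention section: four visits. The protocol gives no correlation between visits, so 0.3, 0.5 and 0.7 are assumed. Equal SDs at all visits are also assumed. The 11-degree difference is taken as given; whether it suits a between-group comparison is a separate matter.

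**Step 1: reproduce the plan's figure.** SD = √((12.5² + 14.9²)/2) = 13.75, and 11/13.75 = 0.80, against 0.799 in magnitude stated. The two-sample t-test then needs 29.1, that is 30 per group, for 85% power. Power at 30 per group is 86.1%. The plan's sample size matches an unadjusted two-group comparison at one visit.

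**Step 2: within-group type I error.** Let ρ be the common correlation between visits and σ² the variance at each visit. With no true change, the mean square for visits has expectation σ²(1 − ρ), while the one-way error mean square has expectation σ². The F ratio is therefore shrunk by a factor of about (1 − ρ). Repeated-measures ANOVA removes the patient effect, so its error term is also σ²(1 − ρ). Simulation with 35 patients, four visits and 40,000 null trials:

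| Assumed ρ | One-way ANOVA | Repeated-measures ANOVA |
|---|---|---|
| 0.3 | 1.23% | 5.1% |
| 0.5 | 0.16% | 4.9% |
| 0.7 | 0.003% | 4.9% |

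**Step 3: within-group power.** Simulation with 35 patients, SD 13.75 and the rise held at all three follow-ups. The 8-degree rise is an assumption. The 11-degree rise is the difference between the two means in the Sample size section.

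| Assumed ρ | 8 degrees: one-way / repeated-measures | 11 degrees: one-way / repeated-measures |
|---|---|---|
| 0.3 | 68% / 85% | 96% / 99% |
| 0.5 | 67% / 95% | 97% / 99.9% |
| 0.7 | 67% / 99.8% | 99% / about 100% |

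**Step 4: between groups at one visit, 30 per group.** The residual variance is multiplied by 1 for the unadjusted test, by 1 − r² for ANCOVA and by 2(1 − r) for change scores, where r is the correlation between baseline and follow-up. Power comes from the noncentral t distribution, with 57 degrees of freedom for ANCOVA.

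| Assumed r | ANCOVA factor | 11 degrees: unadjusted / ANCOVA / change score | 8 degrees (assumed): unadjusted / ANCOVA / change score |
|---|---|---|---|
| 0.3 | 0.91 | 86% / 89% / 73% | 60% / 64% / 47% |
| 0.5 | 0.75 | 86% / 94% / 86% | 60% / 72% / 60% |
| 0.7 | 0.51 | 86% / 99% / 98% | 60% / 87% / 82% |

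The unadjusted 95% confidence interval half-width is 2.00 × 13.75 × √(2/30) = 7.1 degrees. Multiplying by √(1 − r²) gives 6.8 / 6.2 / 5.1 degrees with ANCOVA.

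If change scores were meant, baseline would be used, but with less power than ANCOVA at every correlation shown, and at 0.3 with less than ignoring baseline altogether.

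**Step 5: validity between groups.** In 40,000 null trials the single-visit two-group test rejected 4.8% of the time, with p-values identical to the t-test.

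**The case against.** The strongest reply is that the comparison answering the objective is not in error. The unadjusted test is legitimate in a randomized trial and gives 86% power against 85% planned; covariates are often left to an analysis plan. The gain from adjustment also rests on correlations the protocol does not give, and it is modest at 0.3. All of this stands, and it is why the between-group part is put as a loss of precision. It does not remove the point: the protocol itself names an unadjusted method, and adjustment gains precision at every correlation shown.

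On the within-group part, the reply is that the error is conservative, that it matters little if the change is as large as 11 degrees (96–99% power against 99–100%), and that a null of no change over a year is implausible when both groups are treated. That also stands. The power loss is material for smaller changes, such as the assumed 8 degrees. The p-values are wrong at any size of change.

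Two points of scope are fair. Only the Intervention section mentions within-group comparison, and only for range of motion; the Data analysis section extends the test to all outcomes without mentioning it. And one-way might be loose wording for a one-way repeated-measures ANOVA. The ordinary reading is the independent-groups test, and if another was meant the text still needs correcting.

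**Conclusion.** The concern holds, and the wording should be fixed. As ordinarily read, the named test is wrong for the within-group comparison: true type I error is about 1.2% / 0.2% / below 0.1% instead of 5% at assumed correlations of 0.3 / 0.5 / 0.7. Between groups it is valid, but it gives up a variance reduction of 9% / 25% / 49%. The sizes depend on the assumed correlations and equal SDs. The direction within a group holds for any positive correlation.

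Neither part biases the treatment comparison or undermines the arithmetic of 30 per group. Within-group change cannot show benefit of the added exercise under any test, because both groups are treated and the background itself notes: "Although frozen shoulder is frequently described as a self-limiting condition with gradual spontaneous recovery". The between-group part therefore has the greater bearing on the trial's answer.

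**What to change.** Replace the analysis sentences in the Intervention and Data analysis sections so that they state:

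- **Between groups:** compare groups with adjustment for the baseline value of the outcome, by either ANCOVA at one named visit or a mixed model for repeated measures with group, visit, group-by-visit interaction, baseline and correlated errors within patient. Either is acceptable.
- **Primary visit:** name one before unblinding. The 3-month visit is closest to the 12-week data behind the sample size.
- **Reporting:** give the adjusted between-group difference at that visit with its 95% confidence interval.
- **Within groups:** report change descriptively or with a repeated-measures method, and state that it is not evidence of benefit from the added exercise.

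The cost is analysis wording only. The data are already to be collected, SPSS (already named) fits these models, and neither the sample size nor the visit schedule changes.
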